
Added a 24-week open-label treatment period after the 24-week double-blind treatment period for the IV groups. The purpose of this change was to obtain long-term safety information with continuous exposure of evinacumab IV for up to 48 weeks.
 
As a result, the mandatory 24-week follow-up period for the IV treatment groups was removed to allow patients to go directly into a separate OL study after completing the double-blind treatment period and open-label treatment period. Patients who do not participate in the OL study would enter a 24-week follow up period.
	
Synopsis: Study Design, Study Duration, Treatments
 
Section 3.2.1 Rationale for Study Design
 
Section 3.2.2 Rationale for Dose Selection
 
Section 3.2.3 Benefit/Risk Assessment
 
Section 5.1 Study Description and Duration
 
Figure 1 Study Flow Diagram
 
Section 5.1.1 Description of Study Treatment Groups
 
Section 5.1.2 Follow-up
 
Table 3 Schedule of Events for SC Treatment Group A
 
Table 4 Schedule of Events for IV Treatment Group B
 
Table 7 Follow-up Schedule of Events for IV Treatment Group B
 
Section 10.3.1.2 Modified Intent-to-Treat
 
Section 10.3.2.1 Double-Blind Safety Analysis Set
 
Section 10.3.2.2 Open-Label Safety Analysis Set
 
Section 10.4.1 Patient Disposition
 
Section 10.4.2 Demography and Baseline Characteristics
 
Section 10.4.3.1 Primary Efficacy Analysis
 
Section 10.4.3.2 Secondary Efficacy Endpoint Analysis
 
Section 10.4.3.3 Dose-Response Analysis
 
Section 10.4.3.4 Subgroup Analysis
 
Section 10.4.3.5 Multiplicity Considerations
 
Section 10.4.4 Safety Analysis
 
Section 10.4.4.1 Adverse Events
 
Section 10.4.4.2 Other Safety
 
Section 10.4.4.3 Treatment Exposure
 
Section 10.4.4.4 Treatment Compliance
 
Section 10.4.9.1 First Step: Group B Main Efficacy and Safety Analysis
 
Section 10.4.9.2 Second Step: Group A Main Efficacy and Safety Analysis
 
Section 10.4.9.3 Third Step: Final Safety Analysis

Removed PK sample at week 12 and week 20 for IV treatment Group B
	
Table 4 Schedule of Events for IV Treatment Group B

Change	Sections Changed
For Group A, the ADA at week 12 was removed because ADA is tested at week 4 and week 16 and, therefore, an additional evaluation at week 12 was not considered necessary.	Table 3 Schedule of Events for SC Treatment Group A

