The study consists of 4 (for Group A [SC treatment groups]) or 5 (for Group B [IV treatment groups]) periods: run-in period (for patients whose background LMT has not been stable prior to screening, who are not already receiving a proprotein convertase subtilisin/kexin type 9 [PCSK9] inhibitor antibody, or whose background LMT has not been optimized), a 2-week screening period, a 16-week double-blind treatment period for the SC dose groups or a 24-week double-blind treatment period for the IV dose groups, an approximately 48-week open-label treatment period for the IV dose groups, and a follow-up period that lasts 24 weeks after the last dose of study drug.

Study Duration

The duration of the study for a patient is approximately 41 or 90 weeks, for the SC and IV groups, respectively. This includes the screening, double-blind treatment, open-label treatment (for IV group), and follow-up periods. All patients who successfully complete this study (or successfully complete the double-blind treatment period and open-label treatment period for patients in the IV treatment groups) may have the opportunity to enroll in an open-label extension or safety study. All patients who enroll in the open-label extension or safety study will continue to receive evinacumab.

Population**Sample Size:**

Expected total number of patients is 252 (Group A 144; Group B 108).

Target Population:

Adult men and women, ages 18 to 80, with primary hypercholesterolemia (HeFH*, or non-HeFH with a history of clinical ASCVD) with LDL-C $\geq 70^{**}$ mg/dL (1.81 mmol/L), despite receiving maximally-tolerated LMT. Background LMT would include a stable maximally-tolerated statin and stable PCSK9 inhibitor antibody for patients who are HeFH or non-HeFH with a history of clinical ASCVD. Patients with HeFH not on a statin are allowed to participate if there is documentation of inability to tolerate at least 2 statins.

*HeFH may be diagnosed by at least 1 of the following:

1. Genotyping
2. World Health Organization/Dutch Lipid Network or Simon Broome criteria.

** Efforts will be made to enroll, at a minimum, 25% of patients with LDL-C ≥ 130 mg/dL (3.37 mmol/L). Approximately 25% of the population is targeted to have a baseline LDL-C ≥ 100 mg/dL (2.59 mmol/L).

Please note: To ensure an adequate number of patients with HeFH, randomization will be stratified 2:1 (HeFH:non-HeFH; 24:12) within each treatment group.

Treatment(s)

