The primary endpoint in this study is the percent change in LDL-C from baseline to week 16. As described above, LDL-C is an accepted surrogate endpoint for CV risk, and has repeatedly been used as the primary endpoint for other lipid lowering treatments. The primary endpoint will be assessed at week 16 because that treatment duration will allow all patients in both Group A (SC treatment groups) and Group B (IV treatment groups) to achieve steady state and maximum LDL-C lowering. As such, 16 weeks is an adequate treatment duration to obtain sufficient PK and PD information to guide dose selection.

In addition to providing key information to understand the effect of evinacumab in patients with refractory hypercholesterolemia and to help with dose selection for future studies, long-term safety of IV administrations of evinacumab will be evaluated in Group B patients. For this reason, the double-blind treatment period for Group B is 8 weeks longer than for Group A (24 weeks vs 16 weeks) and a 48-week open-label treatment period will occur for patients in Group B. This additional exposure to evinacumab will help to define further the safety profile for evinacumab.

Long-term safety of SC administration will not be obtained in this study, but patients in Group A may have the opportunity to enroll in an open-label extension or safety study. The SC treatment period in this study is shorter due to the high burden of up to 3 weekly injections, which are administered by study staff at each clinic visit. Therefore, beyond the primary endpoint at week 16, patients will not be required to continue receiving evinacumab injections.

The study design includes a run-in period of variable duration. This run-in period will ensure patients have enough time to become stabilized on their background medications (if they need

stabilization). Since this can vary from patient to patient, depending on the potential changes needed to their background lipid modifying therapy (LMT), the upper limit of the run-in period is variable. Additionally, for all patients not on a PCSK9 inhibitor antibody that will require alirocumab to be provided to them, this change will allow patients to enroll into the study in advance of randomization and start to receive a beneficial lipid lowering therapy.

All patients receiving study treatment will enter a 24-week follow-up period, beginning at the time of the last study treatment administration (double-blind or open-label study treatment).

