5. STUDY DESIGN

5.1. Study Description and Duration

This is a phase 2, randomized, double-blind, placebo-controlled, dose-ranging study to assess varying doses of SC and IV regimens of evinacumab in patients diagnosed with primary hypercholesterolemia (HeFH, or non-HeFH with a history of clinical ASCVD) who have an

LDL-C \geq 70 mg/dL (1.81 mmol/L), despite receiving a stable maximally-tolerated LMT. The LMT would include a stable, maximally-tolerated statin and stable PCSK9 inhibitor antibody for patients who are HeFH or non-HeFH with a history of clinical ASCVD. Patients with HeFH not on a statin are eligible if there is documentation of inability to tolerate at least 2 statins (see Section 7.3 Background Treatments for further information).

The study consists of 4 (for Group A [SC treatment groups]) or 5 (for Group B [IV treatment groups]) periods: a run-in period (for patients whose background LMT has not been stable prior to screening, who are not already receiving a PCSK9 inhibitor antibody, or whose background LMT is not optimized), a 2-week screening period, a 16-week double-blind treatment period for the SC dose groups or 24-week double-blind treatment period for the IV dose groups, an approximately 48-week open-label treatment period for the IV dose groups, and a follow-up period lasting 24 weeks after the last dose of study drug (Figure 1).

All patients in Group B who have successfully completed the double-blind treatment period and the open-label treatment period, and all patients in Group A who have successfully completed the double-blind treatment period and follow-up period in this study may have the opportunity to enroll in an open-label extension or safety study. All patients who enroll in the separate open-label extension study will continue to receive evinacumab.

Figure 1: Study Flow Diagram

Run-in	Screening	Double-Blind Treatment	Open-Label Treatment	Follow-Up Period	
		Group A: SC x 16 weeks Group B: IV x 24 weeks	Group B: IV x 48 weeks	Group A: 23 weeks Group B: 20 weeks	
Variable	(Day -14)	Baseline (Day 1)	End of Double-Blind (Day 113/ Day 169)	End of Open-Label (Approx Day 505)	End of Study (Day 274/ Day 645)

Run-in:

There will be a run-in period for:

- Patients who are not receiving the maximal dose of a PCSK9 inhibitor antibody or whose dose has not been stable for at least 8 weeks before the screening visit
- Patients whose maximally tolerated statin has not been stable for at least 4 weeks before the screening visit

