Randomization will be stratified by high-intensity statin (Yes/No) and HeFH (Yes/No) at baseline. High-intensity statin is defined as rosuvastatin 20 mg or 40 mg daily, atorvastatin 40 mg or 80 mg daily, or simvastatin 80 mg daily (if already on this dose for >1 year). To ensure an adequate number of patients with HeFH are included in this study and exposed to each dose, randomization will be stratified 2:1 (HeFH:non-HeFH; 24:12) within each treatment group.

Investigational medicinal product (IMP) administration during the double-blind treatment period will take place at the site and possibly, by visiting home nurses (only for the SC group). The IMP will be administered at the site on the day of randomization, after all samples for clinical laboratory evaluation have been obtained. In order to ease burden for those patients randomized to receive SC IMP, visiting home nurses may be utilized to administer SC IMP on odd visit dates, eg. Week 1, week 3, and week 5.

Open-Label Treatment Period (Group B only)

Patients in Group B (the IV treatment groups) will enter a 48-week open-label treatment period and all patients will receive evinacumab 15 mg/kg IV Q4W.

Follow-Up Period (Groups A and B)

All patients will be followed for 24 weeks after the last dose of study drug.

Patients should maintain their stable background LMT regimen from screening through the end of study (EOS) visit.

Patients will be reminded to adhere to a heart-healthy diet at screening, and continuing through the EOS visit. Patients should maintain a stable exercise level for the duration of the study, and avoid rigorous exercise 24 hours before each study visit. All lipid results will be blinded from after randomization until the week 36 visit for the IV cohorts, and until database lock for the SC cohorts.

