5.1.2. Follow-up

All patients will be followed for 24 weeks after the last dose of study drug. Thus, for IV cohorts in which the dosing interval is Q4W, patients will be followed for an additional 20 weeks after end of treatment (EOT). For SC cohorts, in which the shortest dosing interval is QW, patients will be followed for an additional 23 weeks after the EOT visit. Patients in Group B may have the option of joining an open-label extension or safety study after successfully completing the treatment period (48 weeks). Patients in Group A may have the option of joining an open-label extension or safety study after successfully completing the treatment period (16 weeks) and follow-up period (24 weeks). Those patients that do not enroll in the separate open-label study will enter a follow-up period, which lasts 20 weeks for IV groups after the last dose of study drug. It takes approximately 24 weeks for evinacumab concentration to be below lower limit of quantitation.

Sexually active patients should be reminded at the EOT visit to maintain highly effective contraceptive measures for 24 weeks after the last dose of study drug. At this visit, women of childbearing potential (WOCBP) may be provided urine pregnancy tests to perform at home with instructions to test for pregnancy 4 weeks after this visit and Q4W thereafter. The patient should also be notified of Q4W follow-up phone calls to confirm contraception use, provide a reminder of pregnancy reporting, and to obtain the results of the pregnancy test.

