4.8.1. Adverse Events Variables

The period of safety observation starts from the time when the patient gives informed consent and continues into the following periods:

- The PRE-TREATMENT period is defined from the day the ICF is signed to the day before the first dose of double-blind study treatment administration.
- The double-blind treatment-emergent adverse event (TEAE) period is defined from the day of the first dose of double-blind study treatment administration to the day of the last dose of double-blind study treatment administration + 168 days (24 weeks) (based on PK considerations, residual effect of study treatment might be observed until 24 weeks after the last dose of study drug) for those patients not proceeding into the OLTP (ie, Group A patients and Group B patients who prematurely discontinue study treatment), or up to the day before the first dose of open-label study treatment administration for those patients proceeding into the OLTP
- The open-label treatment-emergent adverse event (TEAE) period (Group B only) is defined from the day of the first open-label study treatment administration to the day of the last open-label study treatment administration + 168 days (24 weeks).
- The POST-TREATMENT period is defined from the day after the end of the respective TEAE periods to the last study visit.

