5.8.1. Adverse Events

In general, the primary focus of AE reporting will be on TEAEs summarized in respective TEAE periods, specifically the DBTP and OLTP.

If an AE onset date (occurrence, worsening, or becoming serious) is incomplete, an imputation algorithm will be used to classify the AE as pre-treatment, treatment-emergent, or post-treatment. The algorithm for imputing date of onset will be conservative and will classify an AE as treatment-emergent unless there is definitive information to determine pre-treatment or post-treatment status. Details on classification of AEs with missing or partial onset dates are provided in [Section 6.3](#).

Adverse event incidence tables will present the number (n) and percentage (%) of patients experiencing an AE by SOC and PT. In addition, incidence tables by SOC, HLG, HLT, and PT will be provided for all TEAEs, serious TEAEs, and TEAE leading to permanent treatment discontinuation. Multiple occurrences of the same event in the same patient will be counted only once in a table. For tables presenting severity of events, the worst severity will be chosen for

patients with multiple instances of the same event. The denominator for computation of percentages is the respective safety analysis set within each treatment group.

AE incidence tables will present data by SOC sorted alphabetically and PT sorted by decreasing frequency of the pooled evinacumab treated group, and summarize the number (n) and percentage (%) of patients experiencing an AE.

Analysis of all treatment-emergent adverse events

The following TEAE summaries will be generated:

- Overview of TEAEs, summarizing number (%) of patients with any
 - TEAE;
 - Serious TEAE;
 - TEAE leading to death;
 - TEAE leading to permanent treatment discontinuation.
- All TEAEs by primary SOC, HLG, HLT, and PT
- All TEAEs by primary SOC and PT
- Number (%) of patients experiencing common TEAE(s) presented by primary SOC and PT (PT incidence $\geq 5\%$ in any treatment group)
- All TEAEs relationship (related/not related) to evinacumab
- All TEAEs by maximum severity (i.e., mild, moderate or severe)
- For the OLTP only, the event rate per patient-year (the number of patients with an event in question divided by total patient-years) will be provided for all TEAEs by SOC and PT. For a patient with an event, patient-year is censored at time of first event. For a patient without an event, patient-year corresponds to the length of the TEAE period.

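### Open-label adverse event rates per patient-year count event-free patients to last dose + 168 days, even when their last visit in this study, and so routine AE collection, came earlier

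*SAP*

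**What the plan says.** - **Person-time.** SAP 5.8.1 gives an open-label event rate per patient-year by SOC and PT. A patient with the event contributes time to the first event. For the rest: "For a patient without an event, patient-year corresponds to the length of the TEAE period".
- **Length of the period.** SAP 4.8.1 runs the open-label TEAE period from the first open-label dose "to the day of the last open-label study treatment administration + 168 days (24 weeks"). No earlier stop is given. The optional Kaplan-Meier curves in SAP 5.8.1 censor event-free patients at the same point.
- **Data collection.** Protocol 9.4.6 collects AE information until the last study visit. After that, Protocol 9.4.2 requires reporting of SAEs with onset within 30 days of the end-of-study or early termination visit, and later only of fatal or drug-related SAEs.
- **Who is followed.** Protocol 5.1 says "All patients will be followed for 24 weeks after the last dose of study drug", and Protocol 3.2.1 says "All patients receiving study treatment will enter a 24-week follow-up period". Protocol 5.1.2 opens with the same rule but later says "Those patients that do not enroll in the separate open-label study will enter a follow-up period". Extension entry is open to "All patients in Group B who have successfully completed the double-blind treatment period and the open-label treatment period" (Protocol 5.1), whereas Group A must also complete follow-up. The Synopsis, under Study Duration, makes the same distinction.
- **Truncation.** SAP 7.4 cuts the TEAE period at the data cut-off, but only for patients still ongoing at the first or second step analysis.

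**The concern.** Person-time should cover only time when an event would have been recorded. Where the last visit comes before last dose + 168 days, the SAP rule adds time in which a non-serious event could not enter the numerator, so the rate falls. The error does not shrink with more patients.

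Two groups are exposed. Patients lost to follow-up are one: Protocol 6.3 anticipates that some will fail to return. The other is Group B patients who go into the extension at week 72, if they leave this study then. SAP 4.8.1 already handles the analogous transition for the double-blind period, which stops the day before the first open-label dose; nothing matches it at extension entry.

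Long-term IV safety is the stated purpose of the open-label period (Protocol 3.2.1), and this is its only AE summary per patient-year. SAP 5.8.2 gives infusion reactions per administration, a different measure. SAP 7.4 does not repair the final safety analysis, where most of the effect would fall.

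**Working it through.** **Inputs** (Protocol Figure 1 and Tables 4, 5 and 7): first open-label dose day 169; last open-label dose day 477 (week 68); end of open-label visit day 505 (week 72); end of study day 645.

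**Reproducing the plan's figure.** 477 + 168 = 645, the stated end-of-study day. 645 − 505 = 140 days = 20 weeks, the stated Group B follow-up. For a fully followed patient, the TEAE period and observation coincide.

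**One rollover patient with no follow-up here.**
- Counted: C = 645 − 169 + 1 = 477 days.
- Routine AE collection: O = 505 − 169 + 1 = 337 days.
- Excess: 140 days; 140/477 = 29.4%.

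**Group rate.** The numerator is unchanged, so understatement = 1 − (observed time)/(SAP time). The rollover share f is not in the documents and is assumed from 0 to 100%. All rows ignore loss to follow-up, for which the documents give no rate.

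| Case | f = 0% | 25% | 50% | 75% | 100% |
|---|---|---|---|---|---|
| Rare non-serious event, all complete | 0 | 7.3 | 14.7 | 22.0 | 29.4 |
| Rare event, 10% stop early and are followed | 0 | 6.8 | 13.6 | 20.5 | 27.3 |
| Event with 50% incidence over 337 days | 0 | 5.7 | 11.3 | 16.9 | 22.4 |
| Rare SAE captured for 30 days after last visit | 0 | 5.8 | 11.5 | 17.3 | 23.1 |

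Entries are % understatement.
- Row 1: 1 − [f·337 + (1−f)·477]/477.
- Row 2 assumes a last dose at open-label day 155, so 155 + 168 = 323 days are both counted and observed. At f = 1: 1 − (0.1·323 + 0.9·337)/(0.1·323 + 0.9·477) = 1 − 335.6/461.6 = 27.3%.
- Row 3 assumes a constant hazard h = ln 2/337. Observed time is f(1−e^(−337h))/h + (1−f)(1−e^(−477h))/h, and the SAP adds f·e^(−337h)·140. At f = 1: 0.5/h = 243.1 days observed, 70 added, 1 − 243.1/313.1 = 22.4%.
- Row 4 replaces 337 by 337 + 30 = 367, assuming the week 72 visit counts as the end-of-study or early termination visit. At f = 1: 110/477 = 23.1%.
- Fatal or drug-related SAEs: about 0% if all are reported.

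**Patient-years.** If all 108 planned patients complete: 108·477/365 = 141.1 counted. Without routine collection: 108·f·140/365 = 0, 10.4, 20.7, 31.1 and 41.4.

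**Windows.** With the ±3-day visit window (last dose day 480, visit day 502), 480 days are counted and 146 uncovered: 30.4%. With the ±14-day IV dosing window of Protocol 7.1 (last dose day 491, visit day 505), 154/491 = 31.4%. If the last dose is at week 64 (day 449), 112/449 = 24.9%.

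**Against random error.** The exact Poisson 95% interval for 3 events is 0.62 to 8.77 (−79% to +192%). For 54 events, half of 108, it is 40.6 to 70.5 (−25% to +30%). The largest matching biases, 29.4% and 22.4%, lie inside these.

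**The case against.** The strongest reply is that rollover patients may well be followed here. Besides Protocol 3.2.1, 5.1 and the first sentence of 5.1.2, the SAP assumes follow-up for open-label completers: Appendix 10.2, Table 1 sets follow-up windows for them at weeks 4, 12 and 20, and SAP 7.3 runs the final analysis to week 92 for Group B. Neither makes an exception for extension entry. If these passages govern, the rollover bias is 0% and the rule is right for everyone who attends.

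This leaves the premise open without removing it. The later sentence of Protocol 5.1.2, the Group A/Group B contrast in Protocol 5.1 and the Synopsis, and Protocol 8.2.4.2 (which extends antibody follow-up only for patients not entering an open-label study) point the other way. The Amendment 3 rationale does too, but it is change-log text and is not needed. Loss to follow-up is exposed on either reading.

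It is also fair that every non-zero rollover figure needs an assumed share, that extension entry is only a possibility, and that SAP 5.8 makes safety summaries descriptive. These points limit the consequence; they do not make the denominator correct.

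A reader might infer that 29% is the expected error or a hard ceiling. It is neither: it needs every patient to roll over unfollowed, and the permitted windows can push it slightly higher. A reader might also infer that every SOC and PT row is understated. That fails for fatal or drug-related SAEs reported under Protocol 9.4.2, and for pregnancy, which Protocol 9.4.3 requires to be reported for 24 weeks after the last dose.

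**Conclusion.** The concern holds as a defect in the person-time rule: event-free time is credited beyond the last visit. Its size is unknown within a range. It is 0% from rollover if those patients are followed here. Otherwise it is 0 to 29.4% for a rare non-serious event on the nominal schedule, depending on the share who roll over. Loss to follow-up adds an amount that the documents do not allow to be estimated.

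The reach is limited. No hypothesis test uses the rate, it has no concurrent control, n (%) tables do not use person-time, and for a single term the bias is within Poisson error. It should still be fixed, because it is systematic, runs toward lower rates, and costs little to remove. Confidence is medium, since the rollover part rests on a contested reading.

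**What to change.** 1. For the SAP 5.8.1 rate and its Kaplan-Meier censoring, end time at risk at the earliest of last open-label dose + 168 days, last study visit or contact, and any data cut-off. Count in the numerator only events with onset by that date. With everyone rolling over, cutting person-time alone would overstate SAEs captured for 30 days by 367/337 − 1 = 8.9%, and fully captured fatal or drug-related SAEs by 477/337 − 1 = 41.5%.
2. Keep the SAP 4.8.1 period for n (%), PCSV and death tables, and list later-reported SAEs separately.
3. In SAP 4.5, show rollover patients as their own category. Their last visit would be 505 − 477 = 28 days after the last dose, so the 23-week definition counts them as not completing follow-up.
4. Reconcile Protocol 3.2.1, 5.1 and 5.1.2 on who is followed in this study and for how long. Section 5.1.2 gives IV follow-up as 24 weeks after the last dose, 20 weeks after end of treatment, and also 20 weeks after the last dose.

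**Cost.** One SAP rule for two analyses, one listing, one disposition category and minor programming; the protocol text may need an approved amendment (Protocol 15). The rate and n (%) tables may differ by a few late SAEs. A followed patient whose final visit falls 7 days early (day 638) loses 7 of 477 days, or 1.5%; if everyone is followed, rates are otherwise unchanged.
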